Date: Wednesday, November 16, 2016 5:00:11 PM

Print Close

Pro00054122 : A simulation study to assess whether informing physicians of out-of-pocket cost to patients and malpractice history influences ordering. - [name]

View: Study Identification - Identification

VIEW000072

Study Identification Information

This is the first step in your Human Research Application. You will automatically be guided to the appropriate forms needed to complete your submissions.

1.0 * Full Title:

Enter the full study title

Physician use of cost and malpractice information in medical imaging decision making: A deeper look into the factors influencing physician ordering of head CT scans in patients with minor head trauma.

2.0 * Short Title:

Enter a short descriptive title for this study (65 characters maximum):

A simulation study to assess whether informing physicians of out-of-pocket cost to patients and malpractice history influences ordering.

3.0 * Briefly describe the scientific or scholarly rationale:

(i.e. purpose of research)

The purpose of the proposed research is to determine whether the introduction of information regarding litigation history and out-of-pocket cost to patients will influence head CT ordering behavior by Emergency Physicians in a simulated clinical encounter. This research is important as the literature suggests that financial motives and fear of malpractice are two of the most influential factors when Physicians order head CTs. Results from this study will advise future studies and the potential development of targeted clinical decision support for Emergency Physicians. Optimal medical image study ordering will enhance patient safety and potentially save the health system millions of dollars annually.

4.0 * Brief Study Summary

Non-scientific description of the research study, using 3 to 10 sentences:

Statements such as "see protocol" are not acceptable.

Note: Text entered in the Brief Study Summary field will be used to describe your study at www.SCresearch.org, an online directory designed to facilitate recruitment, if inclusion on this site is indicated later in the application.

There is a huge push to cut back on medical spending, lead by the changes in how Medicare reimburses hospitals for patient care. We aim to explore the effects of informing physicians about out-of-pocket patient costs of head CT scans, and educating physicians on the the history of malpractice cases involving failure to order head CT scans.

5.0 * Is this a pilot study?

Yes No

Pro00054122: A simulation study to assess whether informing physicians of out-of-pocket

View: Study Identification - Institutional Review Board

cost to patients and malpractice history influences ordering. - [name]

Institution

- 1.0 * Select the appropriate Institutional Review Board (IRB) for review:
Greenville Health System

Pro00054122: A simulation study to assess whether informing physicians of out-of-pocket cost to patients and malpractice history influences ordering. - [name] View: Study Identification - IRB Review Request

IRB Review Request for Multi-site Studies

The **IRB of Record** is the IRB with the primary responsibility for reviewing a study. For a multi-site study, the internal IRB may serve as the IRB of Record for other sites as well, or they may defer review to another IRB. **If you are requesting one of these IRB reviews, indicate the type below. Otherwise, click Continue on this page.**

IRB OF RECORD IS YOUR INTERNAL IRB

Central Review

- 1.0 The review model where your internal IRB has agreed to serve as the single, central IRB of Record for other sites involved in a multi-site study. Be sure to contact your local IRB to assure that appropriate authorization agreements have been or will be executed.

The institution that allows this in eIRB is MUSC.

* Is this a Central Review?

Yes No

IRB OF RECORD IS ANOTHER IRB

Facilitated Review

- 2.0 The review process used by your local, internal IRB as they make the determination whether or not to accept another IRB's review of a study.

All institutions allow this review in eIRB.

* Is this a Facilitated Review (non-HSSC IRB, non-NCI CIRB, non-contracted IRB)?

Yes No

Independent Review Model

- 3.0 The review model where the NCI CIRB is the sole IRB of Record responsible for both study review as well as review of local context considerations for enrolled institutions.

The institutions that allow this review in eIRB are MUSC, GHS, PH, AnMed and Self Regional.

*** Is this an Independent Review (NCI CIRB)?**

- Yes No

External IRB Review

4.0 The review process used by your local, internal IRB where they defer IRB review to a contracted IRB. The external IRB becomes the IRB of record for all aspects of the study.

The institutions that allow this review in eIRB are MUSC, GHS, SRHS, AnMed and Self Regional.

Yes No

Note: <http://www.hhs.gov/ohrp/humansubjects/guidance/45cfr46.html#46.102>

2.0 * Does this research study involve the investigator obtaining data about living individuals through 1) intervention or interaction with the individual; or 2) identifiable private information? Note: Please check 'Yes' if the study involves a Humanitarian Use Device (HUD).

Yes No

Note: <http://www.hhs.gov/ohrp/humansubjects/guidance/45cfr46.html#46.102>

Pro00054122: A simulation study to assess whether informing physicians of out-of-pocket cost to patients and malpractice history influences ordering. - [name]

View: Training - CITI Training Records

CITI Training Records

Review this information when considering if human subjects research education/training is complete for all investigators and study staff. Personnel training displayed are the current and historical records required by the institution associated with the team member's eIRB user account.

NOTE: All study team members must be in compliance with training requirements prior to beginning any role in the study.

If training is missing or expired:

1. Instructions for completing research education requirements can be found at www.citiprogram.org.
2. Verify this institution's affiliation has been added to the CITI user profile and complete the required training.
3. Verify the first name, last name and preferred email of the CITI user profile matches the eIRB user profile.

The content on this page is provided as a tool to display research training records in real time. These data are routinely updated and are, therefore, current at the present viewing of this content.

6.0 Collaborating Institutions PI(s) CITI Completion Records

Name	Organization	Completed CITI Training
There are no items to display		

Pro00054122: A simulation study to assess whether informing physicians of out-of-pocket cost to patients and malpractice history influences ordering. - [name] View: Training - CITI Course Completion Record - Upload

CITI Course Completion Record - Upload

1.0 A copy of the CITI Course Completion Record for each investigator must be uploaded with this application.

Name	Version	Orig. Author	Orig. Created	Last Modified
[name] Citi Training (Both)	0.01	[name]	4/11/2016 10:12 AM	4/11/2016 10:12 AM
[name] Citi Conflict of Interest	0.01	[name]	3/30/2016 4:58 PM	3/30/2016 4:58 PM
[name] Citi Human Subjects Protection	0.01	[name]	3/30/2016 4:57 PM	3/30/2016 4:57 PM

Pro00054122: A simulation study to assess whether informing physicians of out-of-pocket cost to patients and malpractice history influences ordering. - [name]

View: Review Type - Study Review Type

Study Review Type

Minimal Risk means that the risks of harm anticipated in the proposed research are not greater -- considering probability and magnitude -- than those ordinarily encountered by the general population in daily life or during the performance of routine physical, laboratory, or psychological exams or tests.

1.0 * Requested Review Type

Select the type of IRB review you are requesting.

Exempt

Pro00054122: A simulation study to assess whether informing physicians of out-of-pocket cost to patients and malpractice history influences ordering. - [name] View: Review Type - Exempt Research Category v2.0

Exempt Research Category

Conducting Exempt Research

Research that is exempt from IRB review is not exempt from the ethical principles pertaining to human subject research. All research involving human participants must follow the provisions of applicable regulations and standards regardless of the level or category of review.

Good research design dictates careful consideration of risks/benefits, protections, and informed consent, even if review by the convened IRB does not occur. Moreover, the research design should meet applicable research ethics standards of the investigator's professional association or society. In all cases, the standards of respect for persons, beneficence, and justice enumerated by the Ethical Principles and Guidelines for the Protection of Human Subjects of Research (the Belmont Report) apply to research involving human subjects, whether reviewed or certified as exempt from review.

1.0 * Exemption Category

Choose the exemption category that applies to this research study

None of these categories apply to this research study

Category 1

Research conducted in established or commonly accepted educational settings, involving normal educational practices, such as (i) research on regular or special educational instructional strategies, or (ii) research on the effectiveness of or the comparison among instructional techniques, curricula, or classroom management methods.

Category 2

Research involving the use of educational tests (cognitive, diagnostic, aptitude, achievement), survey procedures, interview procedures or observation of public behavior, unless: (I) information obtained is recorded in such a manner that human subjects can be identified, directly or indirectly through identifiers linked to the subjects; **AND** (ii) any disclosure of the human subjects' responses outside the research could reasonably place the subjects at risk of criminal or civil liability, or be damaging to the subjects' financial standing, employability, or reputation. **Note:** Surveys, interviews, or observations involving children **cannot** be exempt.

Category 3

Research involving the use of education tests (cognitive, diagnostic, aptitude, achievement), survey procedures, interview procedures, or observation of public behavior that is not exempt under Exemption Category (2) of this section if: (i) The human subjects are elected or appointed public officials or candidates for public office; or (ii) federal statutes require, without exception, that the confidentiality of the personally identifiable information will be maintained throughout the research and thereafter.

Category 4

Research involving the collection or study of existing data, documents, records, pathological specimens, or diagnostic specimens, if these sources are publicly available or if the information is recorded by the investigator in such a manner that subjects cannot be identified, directly or through identifiers linked to the subjects.

Category 5

- Research and demonstration projects which are conducted by or subject to approval of [federal] department or agency heads, and which are designed to study, evaluate, or otherwise examine (i) public benefit or service programs; (ii) procedures for obtaining benefits or services under these programs; (iii) possible changes or alternatives to those programs or procedures; or (iv) possible changes in methods or levels of payments for benefits or services under those programs.
-
-

Category 6

- Tests and food quality evaluation and consumer studies, (i) if wholesome food without additives is consumed, or (ii) If a food is consumed that contains a food ingredient at or below the level and for a use found to be safe, or agricultural chemical or environmental contaminant at or below the level found to be safe by the Food and Drug Administration (FDA) or approved by the Environmental Protection Agency (EPA) or the Food Safety and Inspection Service of the U.S. Department of Agriculture (USDA).
-

Note: To qualify for exemption, at least one must be selected

Pro00054122: A simulation study to assess whether informing physicians of out-of-pocket cost to patients and malpractice history influences ordering. - [name] View: Review Type - Exemption Category Justification

Exemption Category

1.0 * Enter Justification

Provide the IRB with information describing your study design and methods. Provide rationale for the exempt criteria chosen on the prior page. Design:

Our research team will be measuring a series of outcome measures related to physician ordering of medical imaging study through a computerized case simulation.

Baseline measure: After presentation of clinical case participants will be asked to select one of three medical imaging study options – two variations of CT scan, and no imaging. Participants have no evidence or other information to advise their selection. The selection of an initial medical imaging study is the baseline measure.

Measure #2 – study ordered when exposed to the Canadian Head CT decision rule: Participants will be provided with information on the sensitivity, specificity, and validation studies that have supported this decision support rule. They will then be given the same imaging options to choose from as the baseline measure – two variations of CT scan, and no imaging.

Measure #3 – study ordering when exposed to malpractice data: Participants will be provided the history of all the cases where physicians were sued for not ordering a head CT scan for patients. With this information, they will be given the option to change which imaging order they would choose in the same case.

Measure #4 – study ordering when exposed to cost information: Participants will be provided information on the cost of a CT order to the patient taken from billing data from the parent institution. They will then be given the three imaging options, and asked what they would choose given

the new information.

Measure #5 – demographic information: We will be collecting basic demographic information on the participants including status (e.g. attending or trainee, military or civilian), age (scaled response not specific age), gender, and years of practice (scaled response from attending physicians).

All data will be collected during the experiment with no planned follow-up activity or engagement with the research participants. The study data, de-identified, will be secured by password in the PI's computer.

Rationale for Exempt criteria:

Simulated cases, presentation of evidence based medicine, and educational opportunities are not only part of medical culture, but are expected to take place at medical centers offering residency training programs in the United States.

Reviewing medical decision making, cost data, and discussing malpractice are topics that are well within the scope of a normal work day for a medical provider.

For these reasons, our research team asserts that there is no more risk to participants of our research study than they would encounter on any given day working in an emergency department.

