2.0 Estimated Study-Wide Enrollment Goal

Enter the anticipated number of subjects to be enrolled at all sites:
200

3.0 * Briefly describe the setting in which the research will be conducted.

The research will be available online at an NIH website, which can be accessed by study participants at their choice of location and electronic device.

4.0 * Participant Remuneration (Payment/Academic Credit)

Will subject(s) receive remuneration?
 Yes No

5.0 * Will prospective participants be vulnerable to coercion or undue influence?

Yes No

If yes, briefly describe additional safeguards included in the protocol to protect the rights and welfare of participants likely to be vulnerable.

6.0 * Identify targeted subject population(s) involved in this research study (Note: The purpose of this question is to determine equitable selection of subjects and to identify vulnerable populations.)

Select all that apply:

Adults (18+)

Males

Females

Pregnant Women

Human Fetuses or Neonates

Minorities

Children (<18 years of age)

Prisoners

Comatose persons

Cognitively Impaired persons

- Terminally Ill persons
- Employees of the principal investigator's institution**
- Students enrolled at the principal investigator's institution
- Non-English speaking persons
- Socially/Economically disadvantaged persons
- Caregivers
- Elderly/Aged persons
- Institutionalized Individuals

7.0 * Study Population

Briefly describe the study population? (e.g. healthy volunteers, adults with Type II Diabetes, children with Asthma):
Emergency Department providers: Doctors, Nurse Practitioners, and Physician Assistants

8.0 * Describe the selection criteria (inclusion/exclusion criteria):

a. Inclusion Criteria: Regardless of assignment to group, basic inclusion criteria include:

- 1) Licensed physician or physician trainee;
- 2) Board certified, board eligible or trainee in Emergency Medicine; and
- 3) Serve as an attending physician or trainee affiliated with the Greenville Health System.

b. Exclusion Criteria: All others not meeting inclusion criteria are excluded.

9.0 * Describe recruitment procedures, including how subjects will be contacted, by whom, and how eligibility will be determined.

Participants will be contacted by the Academic Vice Chair, [name] MD, through their work email address with information about the study and a link to the website where the simulation may be completed.

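### In the only presentation order described, malpractice and cost effects cannot be separated from sequence; if order is randomised, the stated analysis does not use it

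*Protocol*

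**What the plan says.** The protocol's rationale (Study Identification Information, item 3.0) is to "determine whether the introduction of information regarding litigation history and out-of-pocket cost to patients will influence head CT ordering behavior".

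The procedure is in the Exemption Category Justification, item 1.0. A case is shown and a choice made without supporting evidence: "The selection of an initial medical imaging study is the baseline measure". Three information blocks follow, numbered as measures:

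- **Measure #2, decision rule:** "They will then be given the same imaging options to choose from as the baseline measure".
- **Measure #3, malpractice history:** "With this information, they will be given the option to change which imaging order they would choose in the same case".
- **Measure #4, patient cost:** "They will then be given the three imaging options, and asked what they would choose given" the information just added.

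Each block is addressed to participants in general, with no restriction to a group. The section ends: "All data will be collected during the experiment with no planned follow-up activity or engagement with the research participants".

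Two places point to some allocation. The inclusion criteria (Study Subjects, item 8.0) begin "Regardless of assignment to group, basic inclusion criteria include", and the SAP title calls the study a randomized controlled trial. Neither document defines the groups, the randomised factor or the ratio.

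The SAP (Statistical Analysis) compares change in ordering (any CT versus none) by McNemar test with a Bonferroni correction. It does not say which earlier choice each test uses as reference, and it has no order, period or carry-over term. Its chi-square, Fisher and ANOVA comparisons between clinician groups concern demographic and professional characteristics, not ordering.

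**The concern.** Litigation history and out-of-pocket cost are the two factors the study was set up to examine. Information once read cannot be unread, and the clinician revises one decision about one case. Followed as listed, the malpractice response comes only from clinicians who hold the rule, and the cost response only from clinicians who hold both earlier blocks and are choosing for the fourth time.

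The malpractice block reports suits for not ordering a CT, so it plausibly pushes ordering up, while cost plausibly pushes it down. Some of the change at the cost step could then be a retreat from the malpractice step.

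At stake is attribution. A statement that cost information changes ordering, or that one factor matters more than the other, could reflect the sequence to an unknown degree.

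**Working it through.** **1. What the listed order identifies.** Write D for the observed change in the proportion ordering CT at a step, measured against the preceding choice.

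- D(malpractice) = effect of malpractice given the rule + shift from being asked a third time + delayed response to the rule.
- D(cost) = effect of cost given the rule and malpractice + shift from being asked a fourth time + delayed response to, or rebound from, the earlier blocks.

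If all clinicians follow this order, each contributes to the same sum. There is one observed quantity per step and three unknowns. A larger sample narrows the interval around the sum but does not split it. Using baseline as the reference does not help, because the change then also includes the full effect of every earlier block.

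**2. The plan's own sample size.** Inputs from the SAP: p10 = 0.30 (CT to none), p01 = 0.15 (none to CT), power 80%. Alpha is not stated; two-sided 0.05 is assumed.

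n = [z(1−α/2)·√(p10+p01) + z(power)·√(p10+p01−(p10−p01)²)]² / (p10−p01)²

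= [1.960·√0.45 + 0.842·√0.4275]² / 0.15² = 154.6, so 155.

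The SAP's 155 is reproduced. It covers one evidence-versus-no-evidence comparison and has no order component, so it neither supports nor answers this concern.

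**3. What an unmodelled shift does to the test (illustration).** Assumptions not in the documents: a true effect of zero, a net position or carry-over shift of g, and 20% or 45% of clinicians discordant in total (45% is the SAP's 30% + 15%). Then p10 = (total + g)/2 and p01 = (total − g)/2. Probability that the uncorrected McNemar test rejects at n = 155, by enumeration:

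| Shift g | Discordant | α = 0.05 | α = 0.05/3 |
|---|---|---|---|
| 5 points | 45% | 0.15 | 0.07 |
| 5 points | 20% | 0.29 | 0.16 |
| 10 points | 45% | 0.46 | 0.29 |
| 10 points | 20% | 0.83 | 0.68 |

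The divisor 3 assumes three comparisons; the SAP does not give the number.

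**4. The possible readings of the allocation.**

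- *Order fixed:* step 1 applies in full.
- *Order randomised:* McNemar tests pooled over sequences average early and late exposures. They give no first-exposure estimate and no check on carry-over.
- *Groups given different information:* the SAP specifies no between-group comparison of ordering.

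**5. Precision if only first-position data were used.** Power = Φ{[0.15·√n − 1.960·√0.45] / √0.4275}, with the SAP's 30%/15% figures.

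- Swapping malpractice and cost only: 155/2 ≈ 77 clinicians see a given block first. Power is 50%.
- All six orders: 155/3 ≈ 52. Power is 36%.
- Keeping 80% would need about 2 × 155 = 310 or 3 × 155 = 465 clinicians. The study-wide goal is 200 (Study Subjects, item 2.0).

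**The case against.** The strongest reply is that no sentence says the measure numbers are the screen order or that all clinicians see the same order. The group wording and the SAP title suggest that something was allocated, and order is one candidate. The protocol lists a Decision Tree and Simulation Slides (Justification Document, item 2.0) where order and branching could be defined, and these are not in the supplied text. A reader might infer that every clinician certainly met rule, malpractice and cost in one fixed sequence. The documents do not establish that, so this point is conditional.

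A reader might also try to size the bias by noting that fewer CT orders remain to be dropped once the rule has been shown. The documents give no baseline CT rate and no cost-specific switching rate. Such a calculation would also hold the response to cost constant across positions, so it would show no carry-over at all.

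It is also fair that an incremental effect, given earlier information, is a legitimate within-person estimand, and that neither document pre-specifies a claim about cost alone or relative influence. The plan does not say, however, that the incremental effect is the one intended.

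The objection limits how firmly order can be asserted. It does not remove the problem, because none of the three readings in the working has an analysis in the SAP that isolates the two effects.

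**Conclusion.** The concern holds in conditional form. The only order described is baseline, rule, malpractice, cost on one case. If that is how the simulation ran, the malpractice and cost effects cannot be separated from position and carry-over at any sample size. If order was randomised, the stated analysis leaves that unused.

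No size of bias can be derived from the documents. The rejection probabilities in the working show only what a shift of 5 or 10 points would do. They rest on an assumed shift, an assumed discordance and an assumed alpha.

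**What to change.** 1. State the presentation order, what is randomised and what the groups are. Name the reference choice for each McNemar test.
2. If the simulation can still be changed, randomise the order of at least the malpractice and cost blocks for each clinician and log the sequence.
3. Analyse all clinicians with a repeated-measures logistic model (for example GEE) with terms for information type, period and sequence. Report the first-position contrast as a carry-over check, not as the sole estimate.
4. If order was fixed, or data are already collected (the SAP describes recording in the past tense), report each result only as the added effect given the information already shown. Make no claim about cost alone, malpractice alone or their relative influence.

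The cost is minor reprogramming, one stored variable and a slightly more complex analysis. The first-position check will be weak, with about 50% power under two orders at 155 clinicians.

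One limit remains. Every choice after baseline follows some new information, so a shift common to all re-asking stays in each block's change even when order is random. Randomised order frees the comparison between malpractice and cost from position. It does not remove that common shift, and the report should say so.
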